11.4 GLOBAL AMENDMENT 4 CHANGES

Number of global amendment		4.0
Date of CTP revision		18 July 2016
EudraCT number		N/A
BI Trial number		1245.29
BI Investigational Product(s)		empagliflozin
Title of protocol		A randomised, double-blind, placebo-controlled, parallel group, efficacy and safety study of empagliflozin (10 mg, 25 mg) administered orally, once daily over 24 weeks in hypertensive black/African American patients with type 2 diabetes mellitus
To be implemented only after approval of the IRB/IEC/Competent Authorities		
To be implemented immediately in order to eliminate hazard – IRB / IEC / Competent Authority to be notified of change with request for approval		
Can be implemented without IRB/IEC/ Competent Authority approval as changes involve logistical or administrative aspects only		

Proprietary confidential information.

© 2016 Boehringer Ingelheim International GmbH or one or more of its affiliated companies. All rights reserved.

This document may not - in full or in part - be passed on, reproduced, published or otherwise used without prior written permission.

Number of global amendment		4.0
Section to be changed	1	Synopsis; Main criteria for inclusion and 3.3.2 Inclusion criteria
Description of change		
Male and female black/African American patients on diet and exercise regimen alone, or who are EITHER
 
drug-naïve (defined as absence of any oral antidiabetic therapy, glucagon like peptide-1 (GLP-1) analog or insulin for 12 weeks, 16 weeks for pioglitazone prior to randomisation) OR
 
pre-treated with stable dose of
 
 • Metformin only, or • Sulfonylurea only, or • DPP-4 inhibitor only, or • metformin plus sulfonylurea, or • metformin plus DPP-4 inhibitor. 
Treatment has to be unchanged for a minimum of 12 weeks prior to randomization.
 
Dose for metformin: maximum tolerated dose
 
The maximum daily dose of SU or DPP-4 inhibitor should not exceed that stated in the local label
 
note: Patients who were screen failed due to exclusionary anti-diabetic background medication according to versions of the protocol prior to Version 3 (SU, SU+Met, DPP-4 inhibitor, DPP-4 inhibitor+Met) are allowed to be re-screened.

Rationale for change		Administrative clarification, and to maintain consistency of information within the document. Screen failure instructions moved to new section (3.3.5)

Section to be changed	2	3.3 Selection of Trial Population
Description of change		Approximately up to 620 700 patients will be screened for the trial in US.
Rationale for change		Increased number of patients expected to be screened to reflect a higher screen failure rate.

Section to be changed	3	3.3.5 Re-screening
Description of change		Re-screening is permitted for the following categories of screen failed patients only:

Proprietary confidential information.

© 2016 Boehringer Ingelheim International GmbH or one or more of its affiliated companies. All rights reserved.

This document may not - in full or in part - be passed on, reproduced, published or otherwise used without prior written permission.

		
 • Patients who were screen failed due to exclusionary background anti-diabetic therapies (sulfonylurea, DPP4-inhibitor, metformin + sulfonylurea, metformin +DPP4-inhibitor) according to prior versions of the protocol. • Patients who were screen failed due to exclusionary HbA1c 7.0% (53 mmol/mol) -7.4% (57 mmol/mol) at Visit 1 according to prior versions of the protocol. Patients who were screen failed due to exclusionary HbA1c below 7.0% or above 11.0% cannot be re-screened. • Patients who were screen failed due to exclusionary mean seated DBP (Visit 1) according to prior versions of the protocol. However, mean seated SBP (Visit 1) must have been 140-180 mmHg at the previous screening. • Patients who were screen failed due to taking 4 antihypertensive medications (≥ 4 weeks prior to randomization) according to prior versions of the protocol. • Patients who were screen failed due to out-of-window visits prior to ABPM testing (Visit 2.2). If ABPM testing has commenced, no re-screening is permitted. 
A patient who was screen failed due to any of the above screen failure reasons is permitted to be re-screened once only. A new patient number should be assigned to the re-screened patient who should be re-consented. Rationale for re-screening must be document in source documents.
 
Re-screening is not permitted for patients who were screen failed due to other reasons.

Rationale for change		Added subsection to allow re-screen of patients who were screen failed based on the earlier versions of the protocol but would be eligible based on the revised inclusion/exclusion criteria in the subsequent protocol versions.

Section to be changed	4	3.3.6 Repeat test
Description of change		HbA1c test (Visit 1) may be repeated once if the test result from the central lab is exclusionary but the most recent test result from a local lab (taken before Visit 1 but not older than

Proprietary confidential information.

© 2016 Boehringer Ingelheim International GmbH or one or more of its affiliated companies. All rights reserved.

This document may not - in full or in part - be passed on, reproduced, published or otherwise used without prior written permission.

		
one month), if any, falls within the acceptable range.
 
ABPM test (Visit 2.2) may be repeated once if the first attempt is unsuccessful. Refer to Footnote B and Footnote I of the Flow Chart, as well as Section 5.1.2 and Section 6.2.1 for additional details on repeat ABPM.
 
Rationale for all repeat tests must be documented in source documents.

Rationale for change		
To allow confirmatory testing of HbA1c if there is a discrepancy of values between central and local lab results.
 
ABPM re-test is not new. It is repeated in this section for completeness of information.

Section to be changed	5	5.1.1 Endpoints of efficacy
Description of change		Change from baseline in mean seated trough heart rate at 12 weeks of treatment
Rationale for change		Administrative clarification.

Section to be changed	6	5.1.2 Assessment of efficacy
Description of change		
After each ABPM session, the data from the device is to be downloaded and assessed for quality to determine if the session was technically successful.
 
At Visit 2,2 only, if the first session does not pass quality criteria or the mean ABPM SBP is below outside the required range threshold, the session should be repeated. Only one repeat session will be permitted. At Visit 2.2 only, it is important to remember to record the 24-hour mean SBP which is displayed at the bottom of the quality compliance (QC) results. The 24-hour mean SBP at this visit together with a technically successful session determines eligibility for randomization

Rationale for change		Administrative clarification and to maintain consistency of information within the document.

[figure not shown]
Section to be changed	7	5.2.2.2 Adverse event and serious adverse event collection and reporting
Description of change		Added the words “collection and” to the sub title.
Rationale for change		Administrative clarification.

Proprietary confidential information.

© 2016 Boehringer Ingelheim International GmbH or one or more of its affiliated companies. All rights reserved.

This document may not - in full or in part - be passed on, reproduced, published or otherwise used without prior written permission.

Section to be	8	[REDACTED]
---------------	---	------------

Section to be changed	9	6.2.1 Screening and run-in period
Description of change		Visit 1 (Screening) 
 The screening visit is the only visit in this study that does not need to be done fasting. No trial procedures should be done unless the patient has consented to taking part in the trial. Patient identification numbers are available in the RDC system. If a patient is re-screened, a new patient identification number should be assigned.
Rationale for		Added information on patient identification numbers.

Proprietary confidential information.

© 2016 Boehringer Ingelheim International GmbH or one or more of its affiliated companies. All rights reserved.

This document may not - in full or in part - be passed on, reproduced, published or otherwise used without prior written permission.

change		
--------	--	--

Section to be changed	10	6.2.1 Screening and run-in period
Description of change		
Visit 2.2 (Baseline ABPM visit)
 
 Once the data from the session is downloaded, review the QC results to determine if the session was technically successful. Remember to record the 24-hour mean SBP displayed at the bottom of the QC results. The 24-hour mean SBP at this visit together with a technically successful session determines eligibility for randomization. 
If the first ABPM attempt was unsuccessful (failed QC and/or the mean ABPM SBP is below outside the required range threshold), repeat it within 2 days. Patients having two unsuccessful baseline ABPM sessions should not be randomised and must be discontinued.

Rationale for change		Administrative clarification on ABPM repeat, and to maintain consistency of information within the document.

Section to be changed	11	8.4.2

2 LIST OF ABBREVIATIONS

Term	Definition / description
ABPM	Ambulatory blood pressure measurements
AE	Adverse event
AESI	Adverse event of special interest
ALT	Alanine transaminase
ANCOVA	Analysis of covariance
ASA	Acetylsalicylic acid
AST	Aspartate transaminase
ATC	Anatomical-Therapeutic-Chemical classification
BICMQ	BI-customised MedDRA query
BMI	Body mass index
BRPM	Blinded report planning meeting
CI	Confidence interval
CEC	Clinical event committee
CRF	Case report form
CT	Concomitant therapy
CTP	Clinical Trial Protocol
CTR	Clinical Trial Report
DBP	Diastolic blood pressure
DM&SM	Boehringer Ingelheim Data Management and Statistics Manual
DMG	Dictionary Maintenance Group
ECG	Electrocardiogram
EMA	European medicines agency
eCCr	Estimate creatinine clearance
eGFR	Estimated glomerular filtration rate
EoT	End of treatment
FAS	Full analysis set
FPG	Fasting plasma glucose
GI	Genital infection
HbA _{1c}	Glycated haemoglobin

Term	Definition / description
ICH	International Conference on Harmonisation
iPV	Important protocol violation
ITT	Intention to treat
IVRS	Interactive Voice Response System
LOCF	Last observation carried forward
LOCF-IR	Last observation carried forward, including values after rescue
MedDRA	Medical Dictionary for Regulatory Activities
MMRM	Mixed-effect Model Repeated Measures
MQRM	Medical Quality Review Meeting
NCF	Non-completers considered failure
OC	Observed case
OR	Original results
PK	Pharmacokinetics
PPS	Per protocol set
PT	Preferred term
PV	Protocol violation
Q1	Lower quartile
Q3	Upper quartile
RS	Randomised set
SBP	Systolic blood pressure
SCR	Screened set
SD	Standard deviation
SDL	Subject data listing
SMQ	Standardised MedDRA query
SOC	System Organ Class
SSC	Special search category
TBL	Total bilirubin
TOC	Table of contents
TSAP	Trial statistical analysis plan
ULN	Upper limit of normal
UTI	Urinary tract infection

Term	Definition / description
WHO	World health organisation

3 INTRODUCTION

As per International Conference on Harmonisation (ICH) E9, the purpose of this document is to provide a more technical and detailed elaboration of the principal features of the analysis described in the protocol, and to include detailed procedures for executing the statistical analysis of the primary and secondary variables and other data.

This trial statistical analysis plan (TSAP) assumes familiarity with the Clinical Trial Protocol (CTP), including Protocol Amendments. In particular, the TSAP is based on the planned analysis specification as written in CTP Section 7 “Statistical Methods and Determination of Sample Size”. Therefore, TSAP readers may consult the CTP for more background information on the study, e.g., on study objectives, study design and population, treatments, definition of measurements and variables, planning of sample size, randomization.

SAS® Version 9.4 or later version will be used for all analyses.

4 CHANGES IN THE PLANNED ANALYSIS OF THE STUDY

There have been four amendments to the protocol.

The TSAP is written according to the changes reported in protocol amendment 4 ([1](#)) (c01945509-06, 18 JUL 2016).

The following additional endpoints or modifications to pre-specified endpoints have been defined:

[figure not shown]
[figure not shown]
- Urinary tract infections (UTIs), genital infections (GIs), malignancies and volume depletion have been added as AEs of special interest (AESIs)
- Orthostatic blood pressure test result at week 24

5 ENDPOINT(S)

[figure not shown]
Note that several imputation methods will be used for the analysis of efficacy endpoints. Further details can be found in [Section 6.6](#).

Throughout the TSAP, the following should be considered:

- Successful is defined by the vendor BioClinica Inc. as a set of ambulatory blood pressure measurements (ABPM) readings meeting all of the following criteria:
 - Start time must be between 07:00 and 11:00
 - Minimum duration of 24 hours after beginning of the test
 - Minimum of 70% valid readings in the period
 - Total Required Hours is 18 (minimum valid readings for Required Hour is 1)
 - Total Exception Hours is 6 (minimum valid readings for Exception Hour is 0)
 - Total Consecutive Exception Hours is 2
- Valid is defined by the vendor BioClinica Inc. as a reading meeting all of the following criteria:
 - Systolic blood pressure (SBP) between 60 mmHg and 261 mmHg inclusive
 - Diastolic blood pressure (DBP) between 40 mmHg and 151 mmHg inclusive

- 
- Usable is defined as a reading within 24 hours of the beginning of test.
 - All ambulatory endpoints will be calculated by using successful, valid and usable ambulatory blood pressure (BP)/HR readings only. If any ambulatory BP/HR reading is not successful, valid or usable, then the corresponding ambulatory BP/HR measurements will also be set to not successful, valid or usable.
 - All 24-hour means are defined as the mean of hourly means (based on clocktime) of successful, valid and usable readings.
- 

- 
- Mean trough ambulatory BP is defined as the mean of successful, valid and usable readings measured from 22:00 until 23:59 hours after the beginning of the test.
 - Trough seated BP is defined as the mean of the seated/in office vital signs measurements including those taken after the removal of the ABPM device taken on the day of the clinic visit prior to trial drug intake.

- 
- PP is defined as (SBP - DBP).

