At each ABPM visit (Visits 2.2, 5.1 and 7.1), patients are to come to the clinic fasting and the following procedure will be performed. The ABPM device will be attached to the patient and test readings will be taken to check if the device is working properly prior to medication intake. The first test reading is the Beginning of Test reading. Once it has been confirmed that the monitor is properly functioning, study medication will be administered. Record the time the medication was administered and the time the monitor was prompted to take the Beginning of Test reading. The next day when the patient returns to the clinic, the monitor will be prompted to take a Conclusion of Test reading. The device will then be removed and the time of the Conclusion of Test will be recorded. This should be done within 23:30-24 hours of starting monitor.

After each ABPM session, the data from the device is to be downloaded and assessed to determine if the session was successful.

At Visit 2.2 only, if the first session does not pass quality criteria or the mean ABPM SBP is outside the required range, the session should be repeated. Only one repeat session will be permitted. It is important to remember to record the 24-hour mean SBP which is displayed at the bottom of the quality compliance (QC) results. The 24-hour mean SBP at this visit together with a successful session determines eligibility for randomization.

After the removal of the monitor and prior to study medication intake, the patient will be allowed rest for 15 minutes and a seated BP measurement (trough BP) will be taken. The patient will then be given study medication. The time for each of the seated BP measurement, medication intake, and the beginning and conclusion of the 24 hours ABPM readings must be recorded.

Further details on the procedure for BP measurement utilizing ABPM device can be found in the ISF.

Proprietary confidential information.

© 2016 Boehringer Ingelheim International GmbH or one or more of its affiliated companies. All rights reserved.

This document may not - in full or in part - be passed on, reproduced, published or otherwise used without prior written permission.

Blood pressure (seated SBP and DBP)

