- Instruct patient to perform a HBGM once daily during the run-in period in the fasted state and at any time the patient is symptomatic, i.e., experiences signs/symptoms of hyper or hypoglycemia. Instruct patient to contact site immediately if blood glucose reaches the limit described in [Section 4.2.1](#).
- Once all visit procedures are conducted, contact the IRT system to obtain run-in medication kit number and dispense the medication to the patient.
- Administer dose of medication.
- Remind the patient to arrive half an hour earlier for the next scheduled visit (Visit 2.2).
- Instruct patients NOT to take study medication on the morning of the next trial visit.

Visit 2.2 (Baseline ABPM visit)

- ABPM should be done during the run-in period within 7 days prior to Visit 3.
- The ABPM device is attached to the patient and proper operation of the device should be ensured.
- Record the time the medication was administered and the time the monitor was prompted to take the Beginning of Test reading.
- Instruct the patient on the proper use of the ABPM device . The monitor should remain on the patient for at least 24 hours. The patient should be instructed to not remove the monitor and schedule a visit for the next day for removal of the monitor if possible. Patient should arrive early again for the visit on the next day.
- The next day when the patient returns to the clinic (within 23:30-24 hours of the beginning of the test), prompt the monitor to take a Conclusion of Test reading. If an invalid reading occurs for the Conclusion of Test reading, continue to trigger a manual reading until a valid reading is registered. The monitor will then be removed and the time of the Conclusion of Test will be recorded.
- Once the data from the session is downloaded, review the QC results to determine if the session was technically successful. Remember to record the 24-hour mean SBP displayed

Proprietary confidential information.

© 2016 Boehringer Ingelheim International GmbH or one or more of its affiliated companies. All rights reserved.

This document may not - in full or in part - be passed on, reproduced, published or otherwise used without prior written permission.

at the bottom of the QC results. The 24-hour mean SBP at this visit together with a successful session determines eligibility for randomization.

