- If the first ABPM attempt was unsuccessful (failed QC and/or the mean ABPM SBP is outside the required range), repeat it within 2 days. Patients having two unsuccessful baseline ABPM sessions should not be randomised and must be discontinued.
- If ABPM was successful, the patient is eligible for randomization and procedures for Visit 3 can be conducted on the same day after the ABPM device is removed and trough seated blood pressure measurement is taken. If conducted on the same day, procedures for Visit 3 should be done prior to administering study medication.
- Allow the patient to rest for at least 15 minutes after the monitor is removed. Then take a seated blood pressure measurement. Record the time of this measurement. This should be done prior to administering study medication.
- For further instructions for ABPM measurements, please see [Section 5.1.2](#).
- Instruct patients NOT to take study medication on the morning of the next trial visit.

Patients who fail the run-in period following Visit 2 procedures should be registered as a screen failure in the IRT system.

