- Patients should be reminded about the importance of following the agreed diet and exercise plan. Patients should be given a food log to be completed for three consecutive days prior to Visit 5.2 as indicated in the Flow Chart.
- Provide HBGM equipment/supplies and instruct patient on the correct use of HBGM.
- Instruct patient to perform a HBGM once weekly during the treatment period (more frequently if required by local authorities) in the fasted state and at any time the patient is symptomatic, i.e., experiences signs/symptoms of hyper or hypoglycemia. Instruct patient to contact site immediately if blood glucose reaches the limit described in [Section 4.2.1.](#)
- Once all visit procedures are conducted, contact the IRT system to obtain medication kit numbers (Dose escalation kit) and dispense the medication to the patient. Administer dose of study medication.
- Remind the patient to arrive half an hour earlier for the next scheduled visit (Visit 5.1).
- Instruct patients NOT to take study medication on the morning of the next trial visit.

Visit 5.1 (Week 12 ABPM visit)

- ABPM should be done within 7 to 2 days prior to Visit 5.2.
- Attach ABPM device to the patient and initiate the test readings to ensure the monitor is operating properly.
- Administer study medication on the morning of the study visit after the test readings have confirmed that the device is operating properly. Record the time the medication was administered and the time the monitor was prompted to take the Beginning of Test reading.
- Instruct the patient on the proper use of the monitor. The ABPM device should remain on the patient for at least 24 hours. The patient should be instructed not to remove the

Proprietary confidential information.

© 2016 Boehringer Ingelheim International GmbH or one or more of its affiliated companies. All rights reserved.

This document may not - in full or in part - be passed on, reproduced, published or otherwise used without prior written permission.

monitor and schedule a visit for the next day for removal of the monitor. Patient should arrive early again for the visit on the next day.

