- The next day when the patient returns to the clinic (within 23:30-24 hours of the beginning of the test), prompt the monitor to take a Conclusion of Test reading. If an invalid reading occurs for the Conclusion of Test reading, continue to trigger a manual reading until a valid reading is registered. The monitor will then be removed and the time of the Conclusion of Test will be recorded.
- If ABPM was successful, procedures for Visit 5.2 can be conducted on the same day after the ABPM device is removed and trough seated blood pressure measurement is taken. If conducted on the same day, procedures for Visit 5.2 should be done prior to administering study medication.
- If the first ABPM attempt was unsuccessful (failed QC), a repeat reading should be taken within 2 days. Patient having two technically unsuccessful ABPM sessions may continue with Visit 5.2. Procedures for Visit 5.2 can be conducted on the same day after the ABPM device is removed and trough seated blood pressure measurement is taken.
- Allow the patient to rest for at least 15 minutes after the monitor is removed. Then take a seated blood pressure measurement. Record the time of this measurement. This should be done prior to administering study medication.
- Administer dose of study medication.
- For further instructions for ABPM measurements, please see [Section 5.1.2](#).
- Instruct patients NOT to take study medication on the morning of the next trial visit.

Visit 5.2

- BP and orthostatic blood pressure test should always be done before taking any blood samples.
- Collection of urine and blood for laboratory testing must be performed prior to administration of study medication at each visit.
- PK trough sample should be collected within 30 minutes prior to intake of study medication.
- Collect returned medication.
- New medication kit must be dispensed according to the [Flow Chart](#), and the IRT system must be contacted to obtain medication kit numbers to be dispensed.
- Patients should be reminded about the importance of following the agreed diet and exercise plan. Patients should be given a food log to be completed for three consecutive days prior to Visit 7.2 as indicated in the Flow Chart.
- Provide HBGM equipment/supplies and instruct patient on the correct use of HBGM.

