- Instruct patient to perform a HBGM once weekly (more frequently if required by local authorities) in the fasted state and at any time the patient is symptomatic, i.e., experiences signs/symptoms of hyper or hypoglycemia. Instruct patient to contact site immediately if blood glucose reaches the limit described in [Section 4.2.1](#).
- Once all visit procedures are conducted, contact the IRT system to obtain medication kit numbers (Dose escalation kit) and dispense the medication to the patient. Administer dose of study medication.

Proprietary confidential information.

© 2016 Boehringer Ingelheim International GmbH or one or more of its affiliated companies. All rights reserved.

This document may not - in full or in part - be passed on, reproduced, published or otherwise used without prior written permission.

- Instruct patients NOT to take study medication on the morning of the next trial visit.

Visit 6 (Phone visit)

- Remind the patient to arrive half an hour earlier for the next scheduled visit (Visit 7.1).
- Instruct patients NOT to take study medication on the morning of the next trial visit.

Visit 7.1

- ABPM should be done within 7 to 2 days prior to visit 7.2.
- Attach ABPM device to the patient and initiate the test readings to ensure the device is operating properly.
- Administer study medication on the morning of the study visit after the test readings have confirmed that the device is operating properly. Record the time the medication was administered and the time the monitor was prompted to take the Beginning of Test reading.
- The ABPM device should remain on the patient for at least 24 hours.
- Instruct the patient on the proper use of the monitor. The patient should be instructed not to remove the monitor and schedule a visit for the next day for its removal. Patient should arrive early again for the visit on the next day.
- The next day when the patient returns to the clinic (within 23:30-24 hours of the beginning of the test), prompt the monitor to take a Conclusion of Test reading. If an invalid reading occurs for the Conclusion of Test reading, continue to trigger a manual reading until a valid reading is registered. The device will then be removed and the time of the Conclusion of Test will be recorded.

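### Protocol 5.1.2 ends the ABPM session at 23:30-24 h, but the SAP accepts only sessions of 24 h or more, so the two rules meet only at exactly 24:00

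*SAP*

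**What the plan says.** **Protocol 5.1.2.** When the patient returns the next day, the Conclusion of Test reading is prompted and the device is removed. The timing instruction is: "This should be done within 23:30-24 hours of starting monitor".

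**Protocol 6.2.1 and 6.2.2.** At Visit 2.2, "The monitor should remain on the patient for at least 24 hours". At Visits 5.1 and 7.1, "The ABPM device should remain on the patient for at least 24 hours". The same visit instructions give the narrower window for the patient's return: "The next day when the patient returns to the clinic (within 23:30-24 hours of the beginning of the test". The closing reading and removal follow in that instruction without a time of their own.

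**SAP 5.** A session is successful only if it meets every vendor criterion, one of which is "Minimum duration of 24 hours after beginning of the test". All ambulatory endpoints use successful sessions only. At the other end, "Usable is defined as a reading within 24 hours of the beginning of test".

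**Visit 2.2.** Protocol 6.2.1 defines an unsuccessful first attempt there more broadly than the SAP's technical list: "If the first ABPM attempt was unsuccessful (failed QC and/or the mean ABPM SBP is outside the required range), repeat it within 2 days". SAP 6.7 takes the first available successful session at each ABPM time point and ignores any session repeated after a successful one.

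**The concern.** A site that follows 5.1.2 and closes the session at, say, 23:45 has done what the protocol asks, yet the session is not successful under the SAP. The site may also have read, in the visit instructions, that the device should stay on for 24 hours or more.

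The sessions at stake supply hierarchy steps 2 and 3, the week-12 changes in mean 24-hour and mean trough ambulatory SBP. SAP 7.5.1 notes that there is only one post-baseline ABPM assessment up to week 12. A patient with no successful session at Visit 5.1 therefore has nothing on treatment to carry forward, and a failure at step 2 would make steps 3 to 5 exploratory.

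**Working it through.** **1. The plan's own figure.** The point disputes no number in the plan. The figure closest to it is 64 evaluable patients per arm for 24-hour SBP (protocol 7.6: difference 5 mmHg, SD 10 mmHg, 80% power, two-sided 5%). The normal approximation gives n = 2 × (1.960 + 0.842)² × (10/5)² = 62.8, so 63. The t-test gives 63.8, so 64, with power 80.1% at 64 per arm. The figure reproduces, and step 2 has almost no spare power.

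**2. Overlap of the duration rules.**

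| Source | End of session, hours after start |
|---|---|
| Protocol 5.1.2, closing reading and removal | 23:30 to 24:00 |
| Protocol 6.2.1 and 6.2.2, return of the patient | 23:30 to 24:00 |
| Protocol 6.2.1 and 6.2.2, wear time | 24:00 or later |
| SAP 5, successful session | 24:00 or later |

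The first and last rows intersect only at 24:00. In whole minutes, 23:30 to 24:00 holds 30 + 1 = 31 end times. One passes the SAP criterion and 30 fail it. This describes the wording and is not a probability of failure.

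**3. What a short session lacks.** With a reading every 20 minutes (protocol 5.1.2), 24 hours hold 24 × 60 / 20 = 72 scheduled readings, and the two-hour trough window (SAP 5) holds 120 / 20 = 6. Letting the first scheduled reading fall at any whole minute from 0 to 19:

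| Session ends | Scheduled readings kept | Scheduled trough readings kept |
|---|---|---|
| 23:30 | 70-71 of 72 | 4-5 of 6 |
| 23:40 or 23:50 | 71-72 of 72 | 5-6 of 6 |
| 23:59 or 24:00 | 72 of 72 | 6 of 6 |

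These counts omit the prompted closing reading. At a 23:30 removal it falls inside the trough window, so the trough column understates what is available. At worst 70/72 = 97% of scheduled readings remain. Such a session fails on the clock rather than for want of data.

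**4. Route to a missing week-12 value.** The first Visit 5.1 session fails; one repeat is allowed; the repeat fails too; the patient goes on to Visit 5.2. LOCF (SAP 6.6.2.4) needs an earlier on-treatment value, and none exists. Interpolation in the same section needs an observed value before the missing visit, within the on-treatment course; baseline is pre-treatment, and the visible text does not say that it may serve. At Visit 2.2 the consequence differs: two unsuccessful sessions mean that the patient is not to be randomised.

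**5. Scale, by assumption only.** If 5%, 10% or 20% of the 64 per arm had no week-12 value, 60, 57 or 51 would remain (rounded down), with t-test power 77.5%, 75.4% or 70.6%. The documents give no rejection rate, so these are not estimates.

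**6. Visit 2.2 baseline.** Three session sequences lead to an eligible patient: in range at once; QC failure then in range; out of range then in range. Only the third depends on the meaning of *successful*. Under the SAP's technical list the first session would be the baseline; under protocol 6.2.1 it is the repeat.

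**The case against.** Much can be said on the other side.

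- **The return window can be met.** In 6.2.1 and 6.2.2 the 23:30-24 h parenthesis attaches to the patient's return. A patient who arrives at 23:30 and wears the device until 24:00 satisfies the visit instructions and the SAP. This stands. The firm mismatch is between 5.1.2, which times the reading and removal themselves, and the 24-hour rules elsewhere.
- **There is feedback and a second attempt.** Data are downloaded and checked after each session, and a failed session is repeated within 2 days, so losing week 12 takes two failures. This also stands, although a repeat closed under the same 5.1.2 sentence can fail for the same reason.
- **The criterion is the vendor's.** A tolerance may exist in vendor settings or in the site file, neither of which is available. Parts of SAP 5 and 6.6.2 are also not visible. If a tolerance was applied, the visible SAP text misstates the working rule and still needs correcting.

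A reader might infer that sessions were in fact discarded, or that step 2 is underpowered because of this. The documents do not support that: they contain no rejection rate, and the power figures above rest on assumed losses.

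A reader might also infer that SAP 6.7 selects the wrong baseline at Visit 2.2. It does not clearly do so. Its reason for ignoring a second session appeals to the protocol, which calls an out-of-range first session unsuccessful and has it repeated. The general baseline rule in SAP 6.7, the last measurement before randomised drug, points to the same repeat. The choice precedes randomisation, so it would not by itself bias the comparison between arms.

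**Conclusion.** The duration rules conflict as written. Device removal under protocol 5.1.2 and a successful session under SAP 5 coincide only at exactly 24:00, so a session closed as 5.1.2 instructs can be rejected. The consequence for steps 2 and 3 is possible but of unknown size. It requires two failed attempts at Visit 5.1 and a vendor check that enforces 24 hours without tolerance. The conclusion rests on the visible text of both documents.

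The Visit 2.2 question is a clarification and not a separate error. The protocol already points to the in-range repeat. What remains open is the baseline for patients under violation C2.02 (randomised without a successful in-range baseline ABPM), who are excluded from no analysis set. If their only QC-passing sessions were out of range, they have a baseline under the SAP's technical list and none under the protocol's meaning.

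**What to change.** **Duration.** Reconcile the passages to one rule. In protocol 5.1.2, and in the Visit 2.2, 5.1 and 7.1 instructions of 6.2.1 and 6.2.2, state that the Conclusion of Test reading and device removal take place not before 24:00 after the Beginning of Test. Readings beyond 24 hours are already not usable under SAP 5, so nothing that would be analysed is lost. The cost is a few sentences and up to 30 minutes' longer stay for a patient who returns at 23:30. Sessions already closed before 24:00 stay unsuccessful unless the SAP states the tolerance that the vendor actually applied; if there was one, write it into SAP 5 before unblinding.

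**Visit 2.2.** In SAP 6.7, say that *successful* at Visit 2.2 means QC passed and mean SBP 135-175 mmHg, so that an in-range repeat after an out-of-range first session is the baseline. Keep the rule that a session repeated after a successful one is ignored. Name the baseline session for C2.02 patients with no in-range session. This costs two or three sentences.

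A simpler rule, taking the last QC-passing session as the baseline, should not be adopted. It would reverse the handling of repeats that the SAP history table records as clarified on 24 March 2017, and it could replace a qualifying in-range baseline with an out-of-range repeat.
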